6.3.1.1 Scheme of the run-in part

Induction		Consolidation	
1. cycle (2. cycle) at blast persistence		1. cycle	2. cycle
7+3 (HAM elderly)			
7+3	(HAM elderly)	HD-AraC	HD-AraC

6.3.1.2 Treatment schedule for induction chemotherapy

AraC	100 mg/m²/day	continuous infusion over 24 hours	day 1-7
Daunorubicin	60 mg/m²/day	infusion over 1-2 hours	day 3, 4 and 5
Temsirolimus	12.5 mg or 25 mg abs.	infusion over 30-60 minutes	day -1 and 8

6.3.1.3 Decision making on second induction

Bone marrow will be analyzed on day 15:

In case of **morphologic leukemia-free state** (< 5% blasts in an aspirate, no blasts in peripheral blood and no extramedullary disease), no second induction chemotherapy is given. In case of **partial remission** (decrease of bone marrow blast percentage to 5% - 25% and decrease of pretreatment bone marrow blast percentage by at least 50%) or **treatment failure** (no morphologic leukemia-free state, no partial remission), a (second) induction cycle with HAM (elderly) + temsirolimus should be administered on day 22 of first induction chemotherapy if possible.

6.3.1.4 Treatment schedule for induction II chemotherapy

HAM (elderly) induction II for patients with PR or treatment failure:

(cracing) measured in the partition when the cracine is a surface.			
HD-AraC	1g/m² (2 x daily)	infusion over 3 hours	day 1, 3, 5
Mitoxantrone	10mg/m ²	infusion over 30-60 minutes	day 3-5
Temsirolimus	12.5 or 25mg abs.	infusion over 30-60 minutes	day -1 and +8

6.3.1.5 Consolidation therapy I and II

All patients in CR/CRi should receive **two cycles of consolidation chemotherapy**, if conditions described below are fulfilled.

Precondition for consolidation therapy:

CR/CRi with neutrophils $> 1000/\mu l$ and platelets $> 75,000/\mu l$ up to 42 days after last chemotherapy

- Start of consolidation therapy **not earlier than one week and not later than 2 weeks** after confirmation of CR
- If patients' condition does not allow for immediate consolidation chemotherapy it may be postponed for up to 4 weeks after confirmation of CR/CRi
- If patients' condition does not allow for consolidation chemotherapy within 4 weeks from confirmation of CR: observation (depending on treatment arm)

No CRi with neutrophils $> 1000/\mu l$ and platelets $> 75,000/\mu l$ up 35- 42 days after last chemotherapy

• Bone marrow evaluation should be considered from day 35 in order to exclude relapse

CRi with neutrophils $> 1,000/\mu l$ and platelets $> 75,000/\mu l$ between day 43 and day 59

• Reduced dose of temsirolimus or placebo in the forthcoming cycles (for dose reduction see 6.3.3).

No CRi with neutrophils $> 1,000/\mu l$ and platelets $> 75,000/\mu l$ by day 54 - 60

- Bone marrow evaluation should be considered to from day 54 in order to exclude relapse
- Observation. The decision is made by the investigator.

6.3.1.6 Treatment schedule for consolidation chemotherapy I and II

AraC	1g/m² 2 x/day	infusion over 3 hours	day 1, 3 and 5
Temsirolimus	12.5 mg or 25 mg abs.	Infusion over 30-60 minutes	day -1 and 8

6.3.1.7 Maintenance therapy

Patients in the run-in part will not receive temsirolimus maintenance treatment.

6.3.2 Main (controlled) part

After having determined the optimal dose level in the run-in part, the main part of the study will start. In the main part, patients will be randomized between temsirolimus and placebo for induction and consolidation. For maintenance therapy the study will be unblinded. Maintenance therapy is only given in patients randomized in the temsirolimus arm of the study.

Note: For the purpose of clarity, the daily dose of temsirolimus during both induction and consolidation therapy in the main (randomized) part of this protocol is described as 25 mg. However, if the data safety monitoring board (DSMB) decides otherwise, the correct dose of temsirolimus in each part of the protocol will be amended to the protocol for the main part prior to start of the main part.

6.3.2.1 Scheme of the Main (controlled) part

Induction		Consolidation	
1. cycle	(2. cycle) at blast persistence	1. cycle	2. cycle
7+3	(HAM elderly)	HD-AraC	HD-AraC
Temsirolimus/Placebo d -1, 8		Temsirolimus/	Placebo d -1, 8

6.3.2.2 Treatment schedule for induction chemotherapy

AraC	100 mg/m²/day	continuous infusion over 24 hours	day 1-7
Daunorubicin	60 mg/m²/day	infusion over 1-2 hours	day 3, 4 and 5
Temsirolimus/ Placebo	25 mg abs.	infusion over 30-60 minutes	day -1 and 8

6.3.2.3 Decision making on second induction

Bone marrow will be analyzed on day 15:

In case of **morphologic leukemia-free state** (< 5% blasts in an aspirate, no blasts in peripheral blood and no extramedullary disease), no second induction chemotherapy is given. In case of **partial remission** (decrease of bone marrow blast percentage to 5% - 25% and decrease of pretreatment bone marrow blast percentage by at least 50%) or **treatment failure** (no morphologic leukemia-free state, no partial remission), a (second) induction cycle with HAM (elderly) + temsirolimus/placebo will be administered on day 22 of first induction chemotherapy if possible.

6.3.2.4 Treatment schedule for induction II chemotherapy

HAM (elderly) induction II for patients with PR or treatment failure:

HD-AraC	1g/m ² (2 x daily)	infusion over 3 hours	day 1, 3, 5
Mitoxantrone	10mg/m^2	infusion over 30-60 minutes	day 3-5
Temsirolimus /Placebo	25mg abs.	infusion over 30-60 minutes	day -1 and +8

If the duration of the aplasia exceeds 42 days the dose of temsirolimus/placebo should be reduced according to the dose reduction scheme (5.3.5) in these patients for the following temsirolimus/placebo applications.

6.3.2.5 Consolidation therapy I and II

All patients in CR/CRi should receive **two cycles of consolidation chemotherapy**, if conditions described below are fulfilled.

Precondition for consolidation therapy:

CR/CRi with neutrophils $> 1000/\mu l$ and platelets $> 75,000/\mu l$ up to 42 days after last chemotherapy

- Start of consolidation therapy not earlier than one week and not later than 2
 weeks after confirmation of CR
- If patients' condition does not allow for immediate consolidation chemotherapy it may be postponed for up to 4 weeks after confirmation of CR/CRi
- If patients' condition does not allow for consolidation chemotherapy within 4 weeks from confirmation of CR: Maintenance therapy should be started (arm A) or observation (arm B)

No CRi with neutrophils $> 1000/\mu l$ and platelets $> 75,000/\mu l$ at 35 - 42 days after last chemotherapy

 Bone marrow evaluation should be performed between day 35 and 42 to exclude relapse

CRi with neutrophils $> 1,000/\mu l$ and platelets $> 75,000/\mu l$ between day 43 and day 59

• Reduction dose of temsirolimus / placebo should be considered in the forthcoming cycles (for dose reduction see section 5.3.4).

No CRi with neutrophils $> 1,000/\mu l$ and platelets $> 75,000/\mu l$ by day 54 - 60

- Bone marrow evaluation should be considered after day 54 in order to exclude relapse
- Patients may proceed directly to maintenance therapy (arm A) or observation (arm B). The decision is made by the investigator.

6.3.2.6 Treatment schedule for consolidation chemotherapy I and II

AraC	1g/m² 2 x/day	infusion over 3 hours	day 1, 3 and 5
Temsirolimus/ Placebo	25 mg abs.	Infusion over 30-60 minutes	day -1 and 8

6.3.2.7 Maintenance therapy

Maintenance therapy should be started after confirmed CR/CRi with hematological recovery (neutrophils $> 1,000/\mu l$, platelets $> 75,000/\mu l$) from the second consolidation cycle, not earlier than day 28 of second consolidation cycle.

Following unblinding (see section 5.3.4), patients will be administered:

Arm A (temsirolimus) 25mg abs i.v. weekly, for 8 weeks
Arm B (placebo) observation weekly, for 8 weeks

6.3.2.7.2 Arm B (control arm)

Patients will not receive specific maintenance therapy, but will be followed similar to patients treated in arm A.

6.3.3 Dose modification and delays of temsirolimus / placebo

The modifications of temsirolimus or placebo should follow the following pre-defined dose levels:

initial dose:	25 mg abs.
Dose level -1:	20 mg abs.
Dose level -2:	15 mg abs.
Dose level -3:	Discontinue from study

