6.2.5 Dose reduction in standard cytotoxic therapy

In principle, dose reduction of standard cytotoxic therapy is not permitted in this study – with the exception of individual cases in the best interest of the patient. In case that overlapping toxicities of standard cytotoxic treatment and temsirolimus should require a dose reduction, the dose of temsirolimus must be reduced (for dose modification and delay see 6.3.3).

If individual cases of severe toxicities should require an additional dose reduction of standard cytotoxic therapy, the coordinating investigator should first be consulted, if possible, before dose reduction. Dose reduction and reason for dose reduction should be documented. Depending on the toxicities and dose modification, the patient might be withdrawn from the study.

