6.3 Treatment

6.3.1 Run-in part: Dose finding for temsirolimus

In order to address the toxicity profile of temsirolimus added to induction chemotherapy, a **run-in part** with 12 (to 18) patients will be conducted. Patients in this part of the study will be randomized between dose level 1 (12.5mg, n=6) and dose level 2 (25mg, n=6). The optimal dose-level will be determined after 1-2 induction cycles.

After the run-in part, the study will be on hold until the decision by the Data Safety Monitoring Board on dose finding is completed, which may include an additional 6 patients at previously tested or additional dose levels or schedules.

All toxicity during induction therapy will be graded according to the Common Toxicity Criteria for Adverse Events v. 4.0 (CTCAE).

DLT in the run-in part of the trial is defined as:

- CTCAE Grade 4 neutropenia (ANC <0.5 x 109/L) lasting ≥ day 42 after last chemotherapy
- \circ CTCAE Grade 4 thrombocytopenia (platelets < 25 x 109/L) lasting \geq day 42 after last chemotherapy
- CTCAE Grade 3 non-hematologic temsirolimus-related adverse events (excluding hypertension and nausea / vomiting which is not medically managed)

Patients must be evaluable for DLT assessment. Patients with early death during induction due to events unrelated to temsirolimus treatment e.g. infection will not be considered as DLT. Patients with neutropenia or thrombocytopenia due to refractory or recurrent AML will not be considered for DLT. If such cases occur additional evaluable patients will be included.

If < 2 out of 6 patients experience DLT at dose level 2 during induction chemotherapy, dose level 2 will be chosen for temsirolimus during the main part. If > 2 of 6 patients experience DLT at dose level 2 and < 2 out of 6 patients experience DLT at dose level 1, then dose levels 1 will be chosen for temsirolimus during the main part. If 2 out of 6 patients experience DLT at dose level 2 and \leq 2 patients experience DLT at dose level 1, the Data Safety Monitoring Board (DSMB) may opt to include additional 6 patients in dose level 2 of the run-in phase.

Depending on the results, the DSMB may consider an additional dose level to be tested in 6 additional patients or terminate the trial.

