6.3.3.2 Dose modifications for hematological toxicity

Hematological toxicities during the period of chemotherapy and the expected subsequent myelosuppression should only be considered relevant if a grade 4 neutropenia or thrombopenia persists \geq 42 days after start (day 1) of the last chemotherapy cycle. In this case the dose of temsirolimus should be reduced by one dose level for all subsequent chemotherapy cycles and the first two maintenance cycles.

However, different criteria will apply after hematopoietic recovery from the last chemotherapy course during the subsequent maintenance therapy.

Table 1-1 illustrates dose modifications and delays for hematological toxicities during the maintenance therapy:

Table 1-1: Hematological Criteria for Dose Delay and Dose Modification of temsirolimus during maintenance therapy		
Grade	Dose Delay	Dose Modification
Grade 0-2	Treat on time	No Change ^b
Grade 3	Treat on time	DECREASE one dose level c,d
Grade 4	DELAY ^a until ≤ Grade 2	DECREASE one dose level d

Table 1-1: Hematological Criteria for Dose Delay and Dose Modification of temsirolimus during maintenance therapy

- a. If no recovery after 30 days delay, treatment will be discontinued
- b. If ≤ grade 2 toxicity occurs after the first two cycles of maintenance therapy, the dose will be increased by one dose level to a maximum dose of 25 mg. If during the following two maintenance cycles still no grade 3 or 4 toxicity occurs, another dose escalation up to 25mg can be considered.
- c. If the myelosuppression persists for >21 days, the dose will be reduced by one dose level
- d. If dose reduction below dose level -2 is required, treatment will be discontinued

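### The only dose-reduction ladder (25/20/15 mg) has no step for run-in patients who start at 12.5 mg, and the run-in rule that cites it conflicts with the synopsis

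*Protocol*

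**What the plan says.** The run-in (Protocol 6.3.1) has patients "randomized between dose level 1 (12.5mg, n=6) and dose level 2 (25mg, n=6"). The treatment tables keep both doses open throughout: "12.5 mg or 25 mg abs" in induction I (6.3.1.2), and the same two doses in induction II (6.3.1.4) and consolidation (6.3.1.6).

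Two places send these patients to section 6.3.3 for a reduction:

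- Section 6.3.1.5, which belongs to the run-in, orders for CRi reached between day 43 and day 59: "Reduced dose of temsirolimus or placebo in the forthcoming cycles (for dose reduction see 6.3.3").
- Section 6.2.5, which is not confined to either part, says that where overlapping toxicity calls for a reduction, "the dose of temsirolimus must be reduced (for dose modification and delay see 6.3.3").

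Section 6.3.3 stands beside 6.3.1 and 6.3.2 and states no limit of scope: "The modifications of temsirolimus or placebo should follow the following pre-defined dose levels". It lists an initial dose of 25 mg, level -1 at 20 mg, level -2 at 15 mg and level -3: "Discontinue from study". During chemotherapy, persistent grade 4 cytopenia means that "the dose of temsirolimus should be reduced by one dose level for all subsequent chemotherapy cycles" (6.3.3.2). Table 1-2 (6.3.3.3) calls for a one-level decrease after grade 3 or 4 non-hematological toxicity. Its footnote c ends treatment if a dose below level -2 would be needed.

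The synopsis differs in two ways. It prints the ladder under the main part. It also withdraws run-in patients who have not reached CR or CRi with the stated counts by day 42 after the last chemotherapy.

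**The concern.** A reduction rule has to name the dose that follows from each starting dose. Here the run-in text points to a ladder built from 25 mg, while half of the planned run-in patients start below its lowest rung. When one of them meets a trigger, the site is told to reduce but not to what. Sites could then differ: one might stop the drug and another might choose its own dose.

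For late recovery there is a second conflict, because the body of the protocol and the synopsis send the same patient in opposite directions. The run-in exists to describe toxicity at each dose, so what happens after toxicity should be the same at every site.

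**Working it through.** The plan gives no figure to reproduce, so the check is a comparison of doses and a side-by-side reading.

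**Inputs.** Lower run-in dose: 12.5 mg, n = 6 of 12 (6.3.1, 6.3.1.2, 6.3.1.4, 6.3.1.6). Ladder: 25, 20 and 15 mg, then discontinuation (6.3.3).

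**Step 1: each numeric rung against 12.5 mg (rung / 12.5).**

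| Rung | Dose | Ratio | Change |
|---|---|---|---|
| Initial dose | 25 mg | 25/12.5 = 2.0 | +100% |
| Level -1 | 20 mg | 20/12.5 = 1.6 | +60% (+7.5 mg) |
| Level -2 | 15 mg | 15/12.5 = 1.2 | +20% (+2.5 mg) |
| Level -3 | none | not applicable | discontinuation |

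No numeric rung lies below 12.5 mg, so none can serve as a reduction from it.

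**Step 2: what the text yields for a patient at 12.5 mg.** Any cut from 12.5 mg falls below level -2 (15 mg). Table 1-2 footnote c would then end treatment. Alternatively, the ladder's 25 mg anchor means that it does not cover this arm, and the reduction ordered in 6.3.1.5 has no dose. The first reading gives discontinuation, the second an undefined dose. Neither yields the reduced dose that 6.3.1.5 promises for the next cycles.

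**Step 3: who is exposed.** At most 6/12 = 50% of the planned run-in, and of these only patients who meet a trigger and would otherwise continue. The protocol gives no rate for the triggers. If the optional 6 extra patients were all treated at 12.5 mg, the ceiling would be (6 + 6)/18 = 12 of 18.

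**Step 4: late recovery, side by side.** A patient who recovers between day 43 and day 59 has by definition not recovered by day 42. Section 6.3.1.5 gives that patient further cycles at a reduced dose, and the synopsis withdraws the same patient. Both cannot hold. The conflict applies to both run-in arms. Following the synopsis would close only this route to a reduction. The non-hematological route in Table 1-2, as printed in 6.3.3.3, is not limited to the main part and would remain.

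**Step 5: labels.** In 6.3.1, level 1 is 12.5 mg and level 2 is 25 mg. In 6.3.3, level -1 is 20 mg and level -2 is 15 mg. For a run-in patient at 25 mg, one level down is 20 mg on the ladder (20/25 = 0.8, a 20% cut), but 12.5 mg on the run-in scale (12.5/25 = 0.5, a 50% cut). The phrase used in 6.3.3.2 and Table 1-2 therefore has two readings in the run-in.

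**Step 6: does another clause repair it?** Section 6.3.2 and the synopsis provide for an amendment if a dose other than 25 mg is chosen, but only for the main part and before it starts. The run-in precedes that.

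**The case against.** The strongest reply is that no reader would raise a dose on this text. The ladder is anchored to an initial dose of 25 mg, and the operative words order a reduction. Moving a patient from 12.5 to 20 mg therefore follows no instruction. That stands. A reader might infer from the rungs that the plan tells sites to increase the dose after toxicity, but the documents do not support that. They support an undefined step or discontinuation.

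A second reply is that the ladder is main-part text. Its heading names placebo, the run-in has no placebo arm, the 6.3.1.5 bullet also mentions placebo, and the synopsis prints the scheme under the main part. This is a plausible account of how the gap arose. It does not remove the cross-reference in the run-in section, nor the general one in 6.2.5.

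A third reply concerns consequences. A reader might infer that improvised doses at 12.5 mg would distort the choice of dose for the main part. The documents do not show this. The selection rule counts DLTs during induction, while the reduction in 6.3.1.5 acts in consolidation, after that window. Most other triggers, such as grade 4 cytopenia lasting to day 42 and temsirolimus-related grade 3 non-hematological events, are themselves DLTs and so are already counted before any reduced dose is given. What is left is narrow: a reduction at induction II for an event excluded from the DLT definition.

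Finally, the stopping rule in Table 1-1 footnote d, "If dose reduction below dose level -2 is required, treatment will be discontinued", cannot be cited here. That table covers maintenance, which run-in patients do not receive (6.3.1.7). Table 1-2 footnote c states the same rule without that limit.

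**Conclusion.** The point holds as a gap and a contradiction in the reduction rule for the run-in. For patients who start at 12.5 mg, the reduction ordered through 6.3.1.5 and 6.2.5 cannot be carried out from the 6.3.3 ladder: it is undefined or amounts to discontinuation. The ceiling is 6 of the 12 planned run-in patients. The number actually affected depends on how many meet a trigger, which the protocol does not let one estimate. Separately, 6.3.1.5 and the synopsis contradict each other on recovery after day 42, and the two sets of dose-level labels make a one-level step ambiguous.

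The conclusion assumes that 6.3.3 applies to the run-in because the run-in section cites it. If it was never meant to apply, the cross-reference is the error, and the 12.5 mg arm still has no rule. The comparison of EFS in the 200 main-part patients is not touched. The matter concerns safety and costs little to mend, so it is worth settling before the run-in opens.

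**What to change.** Reconcile sections 6.2.5, 6.3.1, 6.3.1.5 and 6.3.3 (with 6.3.3.1 to 6.3.3.3) and the run-in and dose-reduction parts of the synopsis, so that:

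- for each run-in starting dose, the consequence of a reduction trigger is stated once and in the same way everywhere;
- the body and the synopsis agree on what happens to a run-in patient who recovers after day 42;
- the run-in dose levels and the reduction steps carry labels that cannot be confused;
- 6.3.3 says whether it covers the run-in, the main part or both.

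The clinical content of each rule is for the sponsor's clinicians, and none is proposed here. The cost is a wording amendment before the run-in. It does not change the sample size or the analysis of the main part.

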6.3.3.1 General dose modifications

If a dose reduction at dose level -3 is required, the patient should be permanently discontinued from the study treatment.

As a general rule, grade 3 toxicity should be followed by permanent dose reduction of temsirolimus during that therapy phase (chemotherapy phase or maintenance phase). If a grade 3 toxicity during the chemotherapy phase resolves after dose reduction of temsirolimus, the dosage of temsirolimus may be re-escalated after two cycles of maintenance therapy if \leq grade 2 toxicity occurs after the first two cycles of maintenance therapy. If during the following two maintenance cycles still no grade 3 or 4 toxicity occurs, another dose escalation up to 25mg can be considered.

Resolution of an adverse event is defined as disappearance or reduction of the adverse event to < grade 3 toxicity. For patients with grade 2 or greater toxicities present at baseline resolution to at least baseline levels will apply.

6.3.3.2 Dose modifications for hematological toxicity

Hematological toxicities during the period of chemotherapy and the expected subsequent myelosuppression should only be considered relevant if a grade 4 neutropenia or thrombopenia persists \geq 42 days after start (day 1) of the last chemotherapy cycle. In this case the dose of temsirolimus should be reduced by one dose level for all subsequent chemotherapy cycles and the first two maintenance cycles.

However, different criteria will apply after hematopoietic recovery from the last chemotherapy course during the subsequent maintenance therapy.

Table 1-1 illustrates dose modifications and delays for hematological toxicities during the maintenance therapy:

Table 1-1: Hematological Criteria for Dose Delay and Dose Modification of temsirolimus during maintenance therapy		
Grade	Dose Delay	Dose Modification
Grade 0-2	Treat on time	No Change ^b
Grade 3	Treat on time	DECREASE one dose level c,d
Grade 4	DELAY ^a until ≤ Grade 2	DECREASE one dose level d

Table 1-1: Hematological Criteria for Dose Delay and Dose Modification of temsirolimus during maintenance therapy

- a. If no recovery after 30 days delay, treatment will be discontinued
- b. If ≤ grade 2 toxicity occurs after the first two cycles of maintenance therapy, the dose will be increased by one dose level to a maximum dose of 25 mg. If during the following two maintenance cycles still no grade 3 or 4 toxicity occurs, another dose escalation up to 25mg can be considered.
- c. If the myelosuppression persists for >21 days, the dose will be reduced by one dose level
- d. If dose reduction below dose level -2 is required, treatment will be discontinued

